10.0 Privacy/Confidentiality Issues

The patient's information, without identifiers, may be shared with other institutions or universities. [name], his co-investigators, and their staff will comply with any and all laws regarding the privacy of such information. There are no plans to pay the patient for the use or transfer of their de-identified information or specimens.

11.0 Follow-up and Record Retention

The duration of this study is approximately 4 years. We will try to enroll 500 patients during this time. Data collected will be retained indefinitely.

1. Administrative Information

Title	Early Cognitive Intervention in Delirium (ECID)
Trial Registration	https://clinicaltrials.gov/study/NCT04740567
Principal Investigators	[name]., M.Sc. and [name], PsyD
Biostatisticians	[name], MS and [name], MS
Date	Draft Date: November 14, 2024
SAP Version	Version 2.4

2. Introduction

This is the Statistical Analysis Plan (SAP) for the study titled “Early Cognitive Intervention in Delirium (ECID)” randomized trial. This study was sponsored by the National Institute on Aging (5R01AG065249).

3. Background and Rationale

Delirium is a form of acute brain failure that afflicts 17% of older emergency department (ED) and 25% of older hospitalized patients.¹⁻⁴ Delirium is associated with accelerated long-term cognitive decline particularly in patients with Alzheimer’s disease and related dementias (ADRD).⁵⁻¹⁷ Unfortunately, most delirium interventions have been ineffective in improving outcomes.¹⁸⁻²⁰ Cognitive training and rehabilitation may be a feasible intervention to preserve long-term cognition in delirious patients,²¹ but to our knowledge, has not been rigorously evaluated in older hospitalized patients with delirium.

4. Objectives

To address this dearth in knowledge, we conducted a randomized trial with the following objective:

Determine if early (< 24 hours) cognitive training performed twice daily during hospitalization and cognitive rehabilitation performed weekly for 12-weeks post-hospital discharge are associated with improved 4-month global cognition in older delirious patients with and without ADRD. *We hypothesize that early cognitive training and rehabilitation will improve 4-month global cognition in older delirious patients with and without ADRD compared with structured usual care.*

5. Study Population

Table 1 lists the inclusion criteria for ECID randomized trial. Patients were included in the study if they were 65 years or older, hospitalized from the ED, can receive cognitive training within 24 hours of ED presentation, and are delirious. We enrolled patients who were 65 years or older, because delirium disproportionately affects older patients, and they were most likely to benefit from our research. Comatose patients were re-evaluated 1 to 2 hours later. If the coma was persistent, then they were excluded delirium cannot be assessed for in these patients. Additionally, they must be arousable for the cognitive intervention to be administered. Patients who were unable to follow simple commands prior to their acute illness were considered to have end-stage ADRD and may not benefit from our intervention. In addition, our delirium assessment has not been validated for these patients.

Inclusion Criteria	Exclusion Criteria

 • 65 years or older • Admitted through the ED • Cognitive training can be initiated within 24 hours of ED presentation • Delirious at enrollment as determined by the 4AT²² 	
 • Comatose • Not able to follow simple commands or non-verbal prior to the acute illness (end-stage pre-illness ADRD) • Resides in a nursing home • Prisoner • Receiving hospice care • Lives > 100 miles away from the enrolling sites • Non-English speaking • Previously enrolled • Deaf or blind • Intravenous drug, crack or cocaine, or methamphetamine use within the past one year, or any condition that, in the investigator’s opinion, makes them an unreliable trial patient or unlikely to complete the trial. • Psychotic disorder or suicidal gesture requiring hospitalization within the past one year • Discharged from the ED

Table 1. Inclusion and exclusion criteria for ECID randomized trial.

6. Treatment arms

Hospitalized patients with delirium were randomized in 1:2 ratio using permuted block randomization to either cognitive training and rehabilitation intervention or structured usual care defined as follows:

- **Intervention:** Two daily 20-minute cognitive training sessions were administered during hospitalization with the first session occurring within 24 hours of ED presentation. The level of difficulty of the training was tailored to the patient’s current level of cognitive functioning. Cognitive rehabilitation was administered in the patient’s home within 1 week after hospital discharge. Patients received cognitive rehabilitation once a week for 12 weeks with each session lasting approximately 1 hour.
- **Usual care:** Daily delirium assessment without cognitive training occurred during hospitalization. No cognitive rehabilitation was performed in the usual care arm.

7. Outcomes

7.1. Primary outcome at 4-months

The primary outcomes for ECID was global cognition at 4-months, as determined by a comprehensive neuropsychological assessment. Global cognition was assessed for using the **Repeatable Battery for the Assessment of Neuropsychological Status (RBANS)**. The RBANS is a comprehensive neuropsychological battery for the evaluation of global cognition

and has been validated in subjects with mild cognitive impairment, moderate to severe traumatic brain injuries, vascular dementias, and Alzheimer’s disease.²³⁻²⁷ In addition to providing a score for global cognition, it also provides individual scores for immediate and delayed memory, attention, visuospatial construction, and language. Scores range from 40 to 160, with higher scores indicating better cognition.

7.2. Secondary Outcomes at 4-months are listed in Table 2.

Study Assessment	Description
Executive function score	Based on the Delis–Kaplan Executive Function System (D-KEFS) Proverbs subscale (conceptual flexibility), the DKEFS Color Word Interference (inhibition), and DKEFS Verbal Fluency Category Switching subscale (monitoring). ²⁸ Scores range from 1 to 18, with higher scores indicating better executive function.
Older American Resources and Services Activities of Daily Living Scale (OARS ADL) ²⁹	Assesses functional status and is based on 7 basic and 7 instrumental activities of daily living. Scores range from 0 (completely dependent) to 28 (completely independent).
EQ-5D-5L ³⁰⁻³²	EQ-5D-5L characterizes quality of life and contains 5-dimensions (“5D”) related to everyday living: mobility, self-care, usual activities, pain/discomfort, and anxiety/depression. EQ-5D-5L index values, validated for the US population, were calculated, and higher scores represented better quality of life. ³³ An index value score of 1.0 indicates perfect quality of life, whereas a score <0.0 indicates quality of life worse than death. The EQ-5D-5L also asks patients to grade their current global health status from 0 (worst health you can imagine) to 100 (best health you can imagine).
Montreal Cognitive Assessment ³⁴	This is a brief test of global cognition based on attention and concentration, executive functions, memory, language, visuoconstructional skills, conceptual thinking, calculations, and orientation. Scores range from 0 to 30, with higher scores indicating better global cognition.
Mortality	Collected by medical record review or informant interview.
Permanent nursing home placement	Collected by patient or informant interview.

Table 2. Secondary outcomes for ECID.

7.3. Exploratory Outcomes at 4-months are listed in Table 3.

Study Assessment	Description
Individual RBANS subscale domains	Scores for each RBANS individual cognitive will be reported - Immediate and delayed memory, attention, language, visuospatial construction.
Individual D-KEF domains	Individual scores for each DKEF Subscale that make up the Executive Function Composite Score will be reported - Proverbs (conceptual scale flexibility), Color Word Interference (inhibition), and Verbal Fluency Category switching (monitoring).
Clinical Frailty Score ³⁵	Characterizes frailty and is based on comorbidities, functional status, and cognition. This scale ranges from 0 (no frailty) to 9 (terminally ill).
Life Space Assessment ³⁶	Characterizes mobility and physical activity by asking 9 questions characterizing the patient’s movement within his/her environment over the past 3 days.
Rehospitalization	Collected by medical record review or informant interview.

Table 3. Exploratory outcomes at 4 months.

7.3. Index hospital exploratory outcomes

- Delirium duration was defined as the total # of days a patient was delirious or comatose. Delirium was measured daily using the bCAM³⁷ (non-mechanically ventilated) and CAM-ICU³⁸ (mechanically ventilated). We chose the bCAM and CAM-ICU because of their high specificity (>=95%).
- Mean delirium severity throughout hospitalization using the Confusion Assessment Method Severity (CAM-S) scale.³⁹
- Maximum delirium severity throughout hospitalization using the CAM-S
- In-hospital death
- Total number of parenteral (intravenous and intramuscular) doses benzo/antipsychotic medications given during hospitalization adjusting for days in the hospital:
- Hospital length of stay
- ICU length of stay
- Post-discharge disposition in those who survived hospitalization

8. Statistical Methods

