5.2a. Delirium will be assessed for in the ED at screening and 3-hours, and once daily throughout the hospitalization if enrolled for 10 days and at discharge, whichever comes first. Trained CTAs will perform the **modified Brief Confusion Assessment Method (bCAM, 1 minute, Appendix B)** in non-mechanically ventilated patients or the **Confusion Assessment Method for the Intensive Care Unit (CAM-ICU, Appendix C)**. The modified bCAM can be reliably performed by our non-physician research staff. It is 82% to 86% sensitive and 93 to 96% specific for delirium with a kappa of 0.87 indicating excellent interobserver reliability.⁴³ The CTAs will also perform the **Delirium Assessment Battery (Appendix G, 5 minutes)** to capture additional delirium assessments such as the CAM, 3D-CAM, and 4AT for our sensitivity analyses.⁴⁴⁻⁴⁷

5.2.b. Delirium Heterogeneity Factors

Delirium heterogeneity factors will be collected once daily in the ED and hospital to help identify delirium phenotypes using LCA (Aim #3). These heterogeneity assessments do not require any additional patient interaction and arousal, psychomotor activity, and severity can be observed while performing the delirium assessments. **Arousal** will be determined with the **Richmond Agitation Sedation Scale (RASS, Appendix H)**^{48,49} Patients will be categorized as having delirium with normal arousal (RASS = 0), decreased arousal (RASS < 0) or increased arousal (RASS > 0). **Psychomotor activity** will be assessed by using the **Delirium Motor Subtyping Scale-4 (DMSS-4, Appendix I)**.⁵⁰ This observational scale is an abbreviated version of the more complex 11-item Delirium Motor Subtyping Scale (DMSS) with very good agreement (κ = 0.63 to 0.92).^{50,51} Patients will be categorized into hypoactive, hyperactive, mixed, and no psychomotor subtype delirium. **Delirium severity** will be determined by the short form **Confusion Assessment Method Severity (CAM-S, Appendix J)** and will be categorized as none (0 points), low (1 point), moderate (2 points), or severe (3 to 7 points).⁵²

5.2.c. Establishing Pre-illness Cognition and Intelligence

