Secondary analyses will also be performed. We will perform a per protocol analyses; for the multivariable linear regression model, the dose of the interventions (total duration of cognitive training and total duration of cognitive rehabilitation) will be the primary independent variables instead of treatment assignment (cognitive training/rehabilitation versus placebo). We will determine if early cognitive training and rehabilitation are associated with our 4-month secondary endpoints such as the individual RBANS cognitive domains (immediate and delayed memory, attention, language, and visuospatial construction), executive function, functional status, rehospitalization, nursing home placement, and death. We will also determine if early cognitive training reduces delirium duration, hospital length of stay, and discharge to a post-acute care facility. We will also explore if there are specific interventions that potentiate the cognitive intervention's effect such as time-to-cognitive training, discharge to a post-acute care facility, and physical activity during cognitive rehabilitation (mean Life Space questionnaire scores). We will explore if these factors modify the association between the cognitive intervention and 4-month global cognition.

9.2. Data analysis for Aim #2 (fMRI). To test if frontoparietal network connectivity, as characterized by BOLD fMRI, improves with cognitive training/rehabilitation compared with controls, we will apply the co-registered z-statistic maps in a mixed effects model to evaluate regions that differ in activation between the two groups, after separately modeling age, sex, and pre-illness QDRS. Group-level z-statistics and corrected p-values will be reported. As a supplementary analysis, we will also explore whether (i) regional tissue volumes at the imaging MRI time point vary between groups and (ii) cortical perfusion quantified from pCASL varies between groups. For these comparisons, a Wilcoxon rank-sum test or Student's t-test will be applied. With a sample size of 50 (25 per group), we will have sufficient power to detect a 30% improvement in frontoparietal cortex network connectivity with 80% power and a two-sided alpha of 0.05.

9.3. Data Analysis for Aim #3 (identify novel delirium phenotypes using LCA): Aim #3 will use LCA to identify hidden groups based on the observed delirium subtypes

	df
Primary Independent	
Cognitive intervention	1
Pre-illness Cognition / Intelligence	
Pre-illness ADRD	1
Pre-illness QDRS	1

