We will adjust for the same covariates as the primary analysis. However, the number of covariates incorporated will depend on the number patients and events for the proportional odds logistic regression and logistic regression models, respectively. For our proportional odds logistic regression model, we will have one degree of freedom available for every 10 to 15 patients with completed outcome measurements.⁴⁷ For our multivariable logistic regression models, we will have one degree of freedom available for every 10 to 15 outcomes for our multiple logistic regression models.⁴⁷ We will incorporate the covariates in order of importance. Proportions and medians with their IQR will be reported for the intervention and usual groups for categorical and continuous outcomes, respectively. Unadjusted and adjusted odds ratio (aOR) with their 95% confidence intervals (95%CI) will also be reported.

8.6. Analysis for Exploratory Outcomes (4-month and index hospitalization): All exploratory outcomes analyses will be intention-to-treat. For these outcomes, unadjusted comparisons using the Wilcoxon Rank-sum tests or chi-squared test will be performed for continuous and categorical variables, respectively. Unadjusted odds ratios will be reported. A p-value < 0.05 will be considered statistically significant.

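### Delirium duration and hospital and ICU stay have no rule for in-hospital death, so an early death can enter as a good result (exploratory outcomes only)

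*SAP*

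**What the plan says.** SAP 7.3, in its list of index-hospital exploratory outcomes, gives this definition: "Delirium duration was defined as the total # of days a patient was delirious or comatose". Nothing is said about patients who die. "Hospital length of stay" and its ICU counterpart appear as bare list items. "In-hospital death" is a separate item in the same list. The only item limited to survivors is disposition: "Post-discharge disposition in those who survived hospitalization".

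SAP 8.6 states "All exploratory outcomes analyses will be intention-to-treat", and that "unadjusted comparisons using the Wilcoxon Rank-sum tests or chi-squared test will be performed", with p < 0.05 as the significance threshold. Protocol 9.1 shows which direction counts as benefit: "We will also determine if early cognitive training reduces delirium duration, hospital length of stay, and discharge to a post-acute care facility".

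The SAP does rank death worst elsewhere. In sensitivity analysis 3 of SAP 8.3, patients who die before follow-up receive an RBANS score of 39. That rule covers only the primary outcome.

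On the rating window, Protocol 5.2a has delirium assessed "once daily throughout the hospitalization if enrolled for 10 days and at discharge, whichever comes first". SAP 7.3 takes mean and maximum CAM-S over the whole hospital stay and states no window.

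**The concern.** Intention-to-treat keeps in-hospital deaths in the comparison, and the definitions give them whatever they had accrued by the day of death. A patient who dies delirious on day 2 scores 2 delirium days and a 2-day stay. A survivor who was delirious for 4 days scores 4 and stays at least that long. The Wilcoxon test ranks the death as the better result on both outcomes.

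If early deaths were more common in one arm, the test could show a shorter stay, and possibly shorter delirium, in the arm that fared worse. Reporting in-hospital death beside these results lets a reader see the imbalance, but it does not change the direction of the duration or stay comparison.

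**Working it through.** **The plan's own figure.** The SAP gives no figure for delirium duration or stay. Its one calculation (SAP 8.7, RBANS) is used here only for arm sizes.

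- Intervention arm: (1.960 + 0.8416)² × 12.4² × (1 + 1/2) / 6.0² = 7.849 × 153.76 × 1.5 / 36 = 50.3, rounded up to 51.
- Usual care: 2 × 50.3 = 100.6, rounded up to 101. The total is 152, against 153 stated.
- Enrolment: 153 / (0.70 × 0.78) = 280.2, against 282 stated.

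Both agree closely. At 1:2, 282 enrolled gives 94 vs 188.

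**Assumed inputs (not in the documents).**
- In-hospital death: 5% in usual care; 5%, 10% or 20% in the intervention arm.
- No effect on delirium or stay in survivors.
- Delirium days: geometric with mean 4, capped at 10, so the survivor mean is (1 − 0.75¹⁰) / 0.25 = 3.775.
- Mean survivor stay: about 7 days, or 3.775 + 1 + 3 = 7.775 in a second model (delirium days plus 1 plus a Poisson count with mean 3).
- Death day: uniform over the range shown.

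**Shift in the mean.** If survivors average S and deaths average D, an arm with death proportion p has mean (1 − p)S + pD. The difference between arms is therefore (p_int − p_uc) × (D − S). If each patient's own delirium course is cut at death on day d, its mean is (1 − 0.75^d) / 0.25. This is 1, 1.75, 2.3125 and 2.734 for days 1–4, which averages 1.949.

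| Outcome and setting | S | D | 10% vs 5% | 20% vs 5% |
|---|---|---|---|---|
| Delirium, deaths days 1–4, own course cut at death | 3.775 | 1.949 | −0.09 | −0.27 |
| Delirium, deaths days 1–3, delirious until death | 3.775 | 2 | −0.09 | −0.27 |
| Delirium, deaths days 1–10, delirious until death | 3.775 | 5.5 | +0.09 | +0.26 |
| Stay, deaths days 1–4 | 7 | 2.5 | −0.23 | −0.68 |
| Stay, deaths days 1–3 | 7.775 | 2 | −0.29 | −0.87 |
| Stay, deaths days 1–10 | 7 | 5.5 | −0.08 | −0.23 |

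The sign is the sign of D − S. For stay it is negative whenever the average death comes before the average survivor's discharge. For delirium it turns positive once patients who are delirious until death survive, on average, past day 3.775.

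**Planned Wilcoxon test, by simulation.** Percentages are runs with a significant result favouring the arm with more deaths. The nominal value is 2.5%.

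- Equal 5% deaths: 2–3% for both outcomes, so no bias.
- Deaths days 1–4, own course cut at death: about 4% (delirium) and 8% (stay) at 10% vs 5%; about 12% and 39% at 20% vs 5%.
- Deaths days 1–3, delirious until death, second stay model: about 5% and 12%, then 11% and 53%. With a geometric mean of 6 instead of 4: about 6% and 11%, then 21% and 54%.
- Deaths days 1–10, delirious until death: delirium about 1%, then 0.3%, both below nominal.
- Deaths ranked worst, in the days 1–3 settings: false benefit at most 0.6%. Significant harm appears in about 10–11% of runs at 10% vs 5% and 53–54% at 20% vs 5%, for both outcomes.

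**The case against.** The case on the other side has four parts.

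- **Standing of the outcomes.** They are exploratory, tested without adjustment, and used in neither the primary analysis nor the power calculation. In-hospital death is in the same list and 4-month mortality is a secondary outcome, so a large imbalance would be seen. This stands, and it sets the severity.
- **Conditions for bias.** The bias needs excess early deaths in one arm. The protocol describes a minimal-risk behavioural intervention, and no in-hospital death rate is given. The 20% vs 5% case is an extreme. A reader might take the 30% death allowance in SAP 8.7 as support for it, but that figure applies to the 4-month outcome. This also stands.
- **Direction for delirium days.** A reader might infer that the duration definition always turns excess death into apparent benefit. It does not: with deaths over days 1–10 and delirium until death, the count rises in the arm with more deaths. The counterexample does not rescue stay, which still leans shorter (about −0.2 days at 20% vs 5%).
- **The 10-day window.** A reader might infer that duration is silently capped. The limit is stated in Protocol 5.2a and applies to both arms, and the SAP wording about the whole hospital stay concerns CAM-S, not duration. Protocol 5.2.b collects the heterogeneity factors, CAM-S among them, once daily with no 10-day limit, although they are observed during the delirium assessments. The documents therefore do not settle the CAM-S window.

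Replacing the duration outcome outright by delirium-free days would also go too far. That measure mixes death with delirium and assumes no delirium after live discharge. Daily ratings end by discharge, and Protocol 5.1 expects about 30% of subjects to be in post-acute facilities, so the assumption cannot be tested.

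**Conclusion.** The gap is real and limited. As written, an early in-hospital death enters the Wilcoxon comparison as a good result for delirium duration, hospital stay and ICU stay, and no rule in the SAP corrects this. The point is firmer for stay, where every setting examined leaned the wrong way; it would reverse only if deaths came, on average, later than survivors' discharges. For delirium days the direction is not fixed.

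A modest imbalance (10% vs 5%) moves the means by about 0.1 delirium days and 0.2–0.3 stay days. Only a large imbalance (20% vs 5%) produces false benefit often: about 11–21% of runs for delirium and 39–54% for stay when deaths are early. All of this rests on assumed death rates, death timing and distributions. The documents do not show that such an imbalance is expected, and the primary analysis is untouched. The change is optional: a cheap improvement to exploratory outcomes.

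**What to change.** - **Hospital and ICU stay:** in SAP 7.3 and 8.6, give in-hospital deaths the worst rank in the Wilcoxon test, or analyse time to live discharge with death as a competing event.
- **Delirium duration:** keep the defined count as a description, shown beside in-hospital death. Add one comparison, either with in-hospital deaths ranked worst or using days alive without delirium or coma through day 10.
- **Rating window:** reconcile the limit in Protocol 5.2a with the CAM-S wording in SAP 7.3, and state in the SAP which days the duration and CAM-S summaries cover.

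The cost is wording and a derived variable. Daily delirium ratings, length of stay in hours and an expired category for disposition are already among the planned data. The added measures combine death with delirium or stay, so they must be read beside in-hospital death itself. Free days also assume no delirium after live discharge. Because the SAP (draft of November 2024) describes the trial as already conducted, the additions should be labelled as added at that stage.
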